In support of H3, we found that alcohol use strengthens the association of depressive symptoms with suicidal ideation in cross-sectional, observational studies of clinical samples.^{8,29} In support of H4, we found that alcohol expectancies related to mood and disinhibition change the problem drinking-suicidal ideation relation.⁹ In suicide decedents, we found that blood alcohol concentrations positively correlated with suicide means of rapid and high lethality, suggesting that AUA could be seen as reducing fear.³⁰ Similarly, in my cross-sectional and daily diary work (F31), AUA positively correlated with fearlessness and perceived pain tolerance.^{11,23}

Study Participants

A sample of 160 community adults (50% female; 10 pre-pilot; 150 pilot, about 38 per condition) will be recruited from the greater Birmingham area using flyers posted on the UAB campus and on Craiglist.com and Facebook.com (See *Recruitment and Retention Strategy*). Our original target pilot sample size was 120; however, we plan to oversample by 25% to account for the potential that 25% of participants may fail the mood induction. Participants will be told they are volunteering for a study testing "The Effects of Alcohol and Mood on

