Upon reaching a BrAC of at least .075%, a brief manipulation check will be performed. Participants will rate their level of intoxication on a scale of 0 (0=not at all) to 11 (11=more drunk than I have ever been).⁴¹ Immediately after, participants will be randomized to a 10-minute mood induction procedure. A self-referent plus musical mood induction paradigm will be employed to induce a positive or negative mood state in participants.⁴² Self-referent statements (e.g., negative or positive self-statements) and musical mood inductions are both valid, stand-alone procedures for inducing mood. The combination of both has been shown to be effective in inducing a temporary negative mood state in 75% of subjects.⁴² The combined negative mood induction paradigm was created based on a modernized version⁴³ of a seminal, self-referent mood induction⁴⁴ and a musical mood induction.⁴⁵ Participants will read 25 statements presented in a timed, PowerPoint slideshow, first to themselves and then aloud, and are instructed to "feel and experience each statement as it would apply to you personally." They will concentrate on each statement for 20 seconds and then proceed to the next one. Five statements were revised to generalize to the greater population. This is done simultaneously with the musical negative mood induction paradiam, which involves listening to a piece of music that conveys a particular mood (negative: Prokofiev's 'Russia Under the Mongolian Yoke' at half speed; positive: Delibes 'Coppelia'). These musical pieces were chosen as they are the most studied of the effective musical induction procedures.⁴⁶ Subjects will be left alone in the room during the mood induction to lessen inhibitions but will be observed by way of a window.

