Given this is the first known project to examine the effects of AUA, mood, and expectancies on suicide-related attentional bias, our ongoing partial test of the proposed study includes another suicidal bias measure: the Implicit Associations Task-Life/Death (IAT-SI⁴), which measures implicit suicidal cognition. Scores indicate level of identification with life versus death and correlates with suicidal behavior.⁴ We will replace the Stroop with this task if our partial test of the reveals that the mood induction influences IAT-SI scores but not Stroop scores. Even if our proposed pilot study does not find effects of AUA, mood, and expectancies on suicide-related attentional bias, we have a post-manipulation measurement of hopelessness—a strong risk factor for suicide. This secondary dependent variable could serve as the basis for an R01. If in our 10 pre-pilot subjects, the mood induction fails >50% of the time, we will use another effective mood induction (i.e., imaginative film). Further, we are oversampling by 25% (150 subjects instead of 120, in case of 25% mood induction failures). Finally, although our proposed sample may not generalize to suicidal individuals, we believe any effect found in the present study will be larger in a sample of suicidal individuals. This study's strong internal validity offers a strong basis for future studies of individuals with higher levels of distress. Impact. If hypotheses are supported, it would provide strong support for the AAM as it applies to suicide risk. Future studies could test whether decreasing the salience of negative mood or suicide-related expectancies reduces suicide-related attentional bias and thus suicide risk. Possible downstream implications include the potential to inform future basic and applied research examining the effects of AUA on suicide risk. Finally, this project will provide me with the relevant experience to conduct future experiments using alcohol administration to investigate behavioral and affective consequences of AUA.

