COVER PAGE

Official Study Title: Acute Use of Alcohol and Attentional Bias Towards Suicide: An Experimental Test of the Attention-Allocation Model

NCT number: NCT04276779

Date of the document: December 1, 2023

Statistical Design and Power

Statistical Design

Data from Qualtrics (Session 1 baseline data), excel (paper data entered from Session 1 and 2), and DirectRT software will be exported into IBM SPSS statistical software, Version 25. Standard data quality checks and cleaning procedures will be completed. Most notably, any participants voicing awareness of the study aims or not responding adequately to the mood induction will be removed from the initial analyses. Second, manipulation checks will be performed by comparing the participants in the mood conditions on self-reported mood post-manipulation. We expect that negative mood participants will have greater mean scores on the guilt and sadness subscales and lower mean scores on the joviality subscale compared to the positive mood participants.

Study variables for the entire sample will be examined using descriptive statistics such as frequencies and percentages (for categorical variables) and means, standard deviations, and ranges (for continuous variables) to ensure values are reasonable. Prior to conducting analyses related to the hypotheses of the study, individual distributions of continuous variables will be examined visually with histograms to confirm that all assumptions for the analyses are reasonably met. Methods robust to distributional assumptions will be used as appropriate.

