Prior to analysis, Suicide Stroop scores will be evaluated for outliers. We will exclude: trials with incorrect responses, trials with response latencies ± 2 SD from each participant's mean response latency, participants with a mean response latency ± 2 SD from the overall sample's mean, participants whose error rate was +2 SD above the error rate for all participants. We will also examine the reliability, factor structure, and concurrent validity for the suicide-related alcohol expectancies measure (created for this study) prior to its use for Hypothesis 3. We will use exploratory factor analysis (with parallel analysis), Cronbach's alpha, and examine associations with AUDIT total scores and past suicidal ideation severity. Finally, we will confirm there were no pre-existing relevant differences in mood states between our mood and alcohol conditions by estimating measures of association (i.e., R²) between condition assignment and pre-manipulation sad, guilty, and joviality mood states.

Pre-Pilot tests: To finalize study procedures, for the 10 pre-pilot subjects, we will examine prevalence of mood induction effectiveness. If >50% fail the mood induction, we will replace it with another effective mood induction (imaginative film). We will also run frequencies to examine percentage of participants who are successfully deceived, expecting these percentages to be high (>90%). We will use these results to adjust the protocol in order to improve success of our mood manipulation and deception.

Specific Aim 1, Hypothesis 1a: To test the feasibility our experiment, we will first quantify the number of individuals who contact our lab about the study and the percentage who are eligible and participate. We will run descriptive statistics to quantify 1) prevalence of successful mood induction (expecting at least 75%), 2) distress ratings after the study session (expecting average ratings to be low), and 3) number of adverse events (expecting less than 1% of pilot subjects). **Objective 1b:** Using measures of effect size (i.e., Cohen's d, Cramer's V) and t-tests and Chi square analyses, we will examine sociodemographic differences (gender, age, race/ethnicity, income, and alcohol use history) in these feasibility factors.

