For this training grant, as a compromise between feasibility and precision of estimates, I propose to recruit 10 pre-pilot subjects and 150 subjects (approximately 38 per condition combination) over a 2.5-year period. Assuming that 25% of subjects may be excluded due to mood induction failure, we will have 30 subjects per condition. Rather than traditional significance testing, the goal of the project is to examine feasibility and tolerability of procedures and explore observed effect sizes. Inference will be conducted primarily by estimation of 68% confidence intervals to be used as reasonable ranges for observed effect sizes. Following the proposed analysis of Hypothesis 3, it can be shown using variance algebra that the standard error of the effect of alcohol intake on Stroop interference scores within each of the mood induction groups (positive or negative) is $SE_{Alco.Eff} = \sigma \sqrt{2/n}$, where σ is the standard deviation of the Stroop interference scores and *n* is the sample size per condition combination. Thus, the standard error of the differential effect of alcohol intake conditional on mood induction (i.e. the interaction term) is $SE_{Diff.Alco.Eff} = 2\sigma/\sqrt{n}$. With n = 30 and standardizing the Stroop interference scores (i.e. $\sigma = 1$) to express the confidence interval in terms of an effect size (Cohen's d), the half width of a 68% confidence interval for the standardized effect of alcohol intake within each of the mood induction groups is .26 and the half width of a 68% confidence interval for the standardized differential effect of alcohol intake conditional on mood induction is .36, which provide reasonable and tolerable uncertainty ranges.

For completeness, in terms of null hypothesis significance testing (not a primary goal of this study), at a significance level of .05 the sample size provides 80% power to detect a standardized effect of alcohol intake

within each of the mood induction groups of .72, and standardized differential effect of alcohol intake conditional on mood induction of 1.

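### 150 pilot subjects less 25% leaves about 28 per condition, not 30; the precision and power figures computed at n = 30 need a small restatement

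*SAP*

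**What the plan says.** The SAP, under Power and Sample Size Considerations, sets the recruitment: "I propose to recruit 10 pre-pilot subjects and 150 subjects (approximately 38 per condition combination) over a 2.5-year period". It then gives the number left for analysis: "Assuming that 25% of subjects may be excluded due to mood induction failure, we will have 30 subjects per condition". The same section puts n = 30 into its standard-error formulas. It reports 68% confidence-interval half-widths of .26 for the alcohol effect within a mood group and .36 for the alcohol-by-mood interaction, and 80%-power effects of .72 and 1.

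The Protocol shows where 150 came from. Under Study Participants the pilot target had been 120, and "we plan to oversample by 25% to account for the potential that 25% of participants may fail the mood induction". The section on potential problems repeats it: "we are oversampling by 25% (150 subjects instead of 120, in case of 25% mood induction failures".

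The 25% matches the literature rate in the Protocol's Procedures, where the combined induction is described as "effective in inducing a temporary negative mood state in 75% of subjects". It also matches the SAP's feasibility expectation under Specific Aim 1 of at least 75% success.

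**The concern.** Raising a target by 25% does not protect it against a 25% loss, because the loss is taken from the larger number. The stated 30 per condition is exactly the old target (120/4), so it looks carried over and not calculated from 150 and 25%.

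The SAP makes interval estimation its main form of inference and describes these half-widths as acceptable. They should therefore correspond to the loss that the SAP itself assumes. The pilot is also meant to inform the design of later studies, so the inflation rule could be copied forward.

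**Working it through.** **Inputs.** From the SAP, Power and Sample Size Considerations: 150 pilot subjects, about 38 per condition; 25% excluded; SE = σ√(2/n) for the alcohol effect within a mood group and 2σ/√n for the interaction; σ = 1; 68% intervals; significance level .05; power 80%. From the Protocol: four between-subjects conditions and an original target of 120. Assumptions: equal loss across conditions unless stated, a two-sided test (the SAP does not give sidedness) and normal quantiles.

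**Number remaining**
- 150 × 0.75 = 112.5, and 112.5/4 = 28.1 per condition.
- From the rounded cell size: 38 × 0.75 = 28.5.
- Stated: 30 per condition, 120 in total.

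**Source of the gap**
- As done: 120 × 1.25 = 150.
- Needed to keep 120 after a 25% loss: 120/0.75 = 160.
- Largest loss that 150 can absorb: 1 − 120/150 = 20%.

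**Precision and power.** The half-width is 0.99446 × SE, and the 80%-power effect is (1.960 + 0.842) × SE = 2.8016 × SE.

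| n per condition | Half-width, within mood group | Half-width, interaction | 80%-power effect, within mood group | 80%-power effect, interaction |
|---|---|---|---|---|
| 30 (SAP) | .257 | .363 | .723 | 1.023 |
| 28.5 | .263 | .373 | .742 | 1.050 |
| 28.1 | .265 | .375 | .747 | 1.057 |

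The first row reproduces the SAP's .26, .36, .72 and 1 (the last rounded down from 1.02). The formulas are therefore sound, and the only faulty input is n. The standard-error ratio is √(30/28.125) = 1.033. Power at the stated effects of .72 and 1 is 79.6% and 78.2% at n = 30, and 77.0% and 75.5% at 28.1.

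**Other readings that might give 30**
- *Counting the 10 pre-pilot subjects.* 160 × 0.75/4 = 30, but both documents count them apart from the 150, the SAP uses them to finalise procedures, and the Protocol ties the 25% to 150 versus 120.
- *Loss in the negative-mood conditions only.* The literature rate concerns a negative mood state, and the Protocol gives none for the positive induction. The conditions then hold 28.1 (negative) and 37.5 (positive), again not 30. The interaction SE is √(2/28.125 + 2/37.5) = .353. Half-widths are .265 (negative), .230 (positive) and .351 (interaction); 80%-power effects are .747, .647 and .988.

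**The case against.** The strongest objection is that this is editorial. The half-widths move by .008 and .012. From the SAP's rounded 38 per condition, the within-group value still prints as .26. The SAP sets no precision threshold, calls the sample a compromise with feasibility and treats significance testing as secondary. All of this stands, and it is why the point is minor. Part of the visible difference is also rounding: the printed 1 for the interaction is already 1.023 at n = 30, so the like-for-like change is to 1.057.

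The direction of the change also depends on the reading. If only the negative-mood conditions lose subjects, the interaction figures are slightly better than stated, while the negative-mood figures are still slightly worse. Equal loss is the more natural reading, because the SAP and the oversampling sentences apply the 25% without restriction.

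The 25% is a contingency and may not occur. In the Protocol's partial test, mood-induction and deception failures together were 6 of 34 (17.6%), below the 20% break-even. But the sentence assumes 25% and states a result, and that result is wrong for that assumption.

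Finally, 28 may not be the analysed number either. The SAP says that "any participants voicing awareness of the study aims or not responding adequately to the mood induction will be removed from the initial analyses", and it adds latency and error-rate exclusions. The partial test kept 23 of 34 for the Stroop analysis. If that retention held here, which is an assumption, 150 × 23/34/4 = 25.4 per condition would remain, with half-widths of .279 and .395. Conversely, later analyses that restored all 150 would give .230 and .325. Both shifts exceed the one from 30 to 28. This is a reason to mention the other exclusions, not to leave the arithmetic uncorrected.

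**Conclusion.** The concern holds. At the SAP's own assumptions, 112.5 subjects remain, 7.5 fewer than the implied 120, or about 28 per condition. No reading supported by the documents gives 30. Under equal loss, standard errors are about 3% larger than stated. The claim is that the stated n does not match the stated contingency, not that 28 is the number to expect. No analysis or conclusion of the pilot depends on it, so it is a minor correction that should be made.

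**What to change.** In the SAP, Power and Sample Size Considerations, replace the sentence on the remaining n and its dependent figures with wording such as: *If 25% of the 150 pilot subjects are excluded for mood induction failure, about 112 remain (about 28 per condition, assuming equal loss). The 68% half-widths are then about .265 within a mood group and .375 for the interaction, and the 80%-power effects about .75 and 1.06.* Three decimals for the half-widths keep rounding from exaggerating the change.

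In the Protocol, under Study Participants and in the section on potential problems, replace the oversampling rationale with: *150 instead of 120 keeps 30 per condition if losses are at most 20%.* This agrees with the corrected SAP paragraph, which shows what remains at 25%.

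Optionally, add without a figure that the 25% covers mood induction failure only, and that the exclusions for awareness of the aims, response latency and error rate come on top.

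The cost is wording in one SAP paragraph and two Protocol sentences. Under equal loss the stated figures become slightly less favourable. Enrolment and the analysis do not change.

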Preliminary Data

Preliminary work has provided partial support of H1 regarding feasibility of the study. We are conducting a partial test of our experiment (without alcohol administration) with a community sample examining the effects of the mood induction on mood and suicide-related attentional bias (Launched 10/11/19; currently paused due to COVID19 safety concerns). Using similar recruitment procedures, 86 individuals have been screened; 55 met inclusion criteria; 41 attended a study session; 35 remained eligible after in-person screening; 1 withdrew before completing the procedures. Thus, we had preliminary data from 34 participants. There was group equivalence in mood prior to mood induction (ps = .39-.81). *T*-tests revealed effectiveness of the mood induction. The negative mood group reported higher post-manipulation sadness (p=.001, Cohen's d=1.24) and guilt (p=.001, d = 1.21) and guilt (p=.001, d = 1.21)

and lower joviality (p=.05, d = .68) compared to the positive mood group. These were medium to large effects despite 5 participants claiming the mood induction was ineffective in post-study interviews.

Preliminary analyses showed that the distribution and variability in the suicide-related attentional bias scores (M=10.17, SD=41.32) were similar to that of prior studies²⁸ of nonsuicidal subjects (M=3.96, SD=58.48, d=0.12). Preliminary analyses supported the anticipated direction of effect of mood on suicide-related attentional bias. The sample size for this analysis was reduced to 23 due to missing data on Stroop (software malfunction, n=2), mood induction and study aims deception failure (n=6), and exclusion of error trials (reducing analysis sample by 5). Although not statistically significant, the negative mood group showed more suicide-related attentional bias (M=15.77, SD=31.33) than the positive mood group (M=2.45, SD=48.24, d=.32). The negative mood group also had more depressive-related attentional bias (M=4.83, SD=58.48) than the positive mood group (M=-6.70, SD=41.96, d=.23). These data provide empirical support for the proposed study aiming to further test the feasibility of our procedures and hypotheses guided by the AAM.

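### The loss allowance behind 30 per condition counts only mood-induction failure, so the stated precision and detectable effects are moderately too favourable

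*SAP*

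**What the plan says.** **The allowance.** The SAP, Power and Sample Size Considerations, sets enrolment: "I propose to recruit 10 pre-pilot subjects and 150 subjects (approximately 38 per condition combination) over a 2.5-year period". It then goes straight to the analysed sample: "Assuming that 25% of subjects may be excluded due to mood induction failure, we will have 30 subjects per condition". The protocol, Study Participants, gives the same single reason: "we plan to oversample by 25% to account for the potential that 25% of participants may fail the mood induction", with an original target of 120. The 25% matches a figure in the protocol's description of the induction: "The combination of both has been shown to be effective in inducing a temporary negative mood state in 75% of subjects".

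**The figures built on it.** At n = 30 per condition the SAP gives 68% confidence-interval half-widths of .26 (alcohol effect within a mood group) and .36 (interaction). It gives effects detectable with 80% power of .72 and 1.

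**The removals.** The SAP, Statistical Design, lists more than mood failure:

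- on awareness and mood: "any participants voicing awareness of the study aims or not responding adequately to the mood induction will be removed from the initial analyses"
- on speed: anyone whose average latency lies more than 2 SD either side of the sample average is dropped
- on accuracy, it excludes "participants whose error rate was +2 SD above the error rate for all participants"

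**The partial test.** The protocol, Preliminary Data, describes a run of the procedures without alcohol that yielded data from 34 participants. For the attentional-bias comparison: "The sample size for this analysis was reduced to 23 due to missing data on Stroop (software malfunction, n=2". The same sentence adds 6 for mood-induction and deception failure together, and 5 for the exclusion of error trials.

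**The concern.** The allowance covers one reason for leaving the analysis set, but the SAP's own rules supply three more at participant level: awareness of the aims, outlying mean latency and high error rate. Lost Stroop data is a further source, and it occurred in the partial test. No allowance is made for any of these.

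Precision is the main quantitative argument for the sample size, because the plan infers mainly from 68% intervals. If fewer than 30 per condition are analysed, those intervals will be wider than the SAP tells its readers to expect. The plan is also a feasibility study, so the proportion of enrolled participants who give usable Stroop data is something a later trial would want to know.

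**Working it through.** **Inputs.** 150 enrolled in four conditions (37.5 each); 25% mood-induction failure; standardised SD of 1; alpha .05, taken as two-sided because that reproduces the SAP. Partial-test counts: 34 participants, 23 analysed, with losses listed as 2, 6 and 5.

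**Formulas.** With n per condition, SE = √(2/n) for the alcohol effect within a mood group and 2/√n for the interaction, as in the SAP. The 68% half-width is .994 × SE. The effect detectable with 80% power is (1.960 + .842) × SE = 2.80 × SE. Power at an effect d is Φ(d/SE − 1.96), a normal approximation.

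**Reproducing the plan at n = 30.** √(2/30) = .258 and 2/√30 = .365. The half-widths are .257 and .363 and the detectable effects .723 and 1.023. The stated .26, .36, .72 and 1 therefore follow, given n = 30.

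**From 150 to 30.** Four conditions of 30 make 120, and 120/150 = .80, so total loss from all causes must be 20%. The 25% gives 150 × .75 / 4 = 28.1. (150 is 120 × 1.25; keeping 120 after a 25% loss would take 120/.75 = 160.)

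**Adding the uncounted losses.**

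- *Two 2-SD rules.* Under normality, 4.55% lie beyond ±2 SD on mean latency and 2.28% above +2 SD on error rate. With independence the combined loss is 1 − .9545 × .9772 = 6.7%. With 25% mood failure: 150 × .75 × .9327 / 4 = 26.2.
- *Partial-test total.* 11/34 = 32.4%, exact 95% CI 17% to 51%. 150 × 23/34 / 4 = 25.4. This total already includes mood and deception failure.
- *Partial-test listed counts.* 2 + 6 + 5 = 13, and 13/34 = 38.2%. 150 × 21/34 / 4 = 23.2.
- *Low-loss case.* Mood and deception failure at the partial-test rate of 6/34 (17.6%), plus the 6.7%: 150 × 28/34 × .9327 / 4 = 28.8.

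| Scenario | Total loss | n per condition | Half-widths | Detectable effects | Power at .72 and at 1 |
|---|---|---|---|---|---|
| As stated | 20% | 30 | .257, .363 | .72, 1.02 | 80%, 78% |
| Low-loss case | 23% | 28.8 | .262, .371 | .74, 1.04 | 78%, 77% |
| 25% mood failure only | 25% | 28.1 | .265, .375 | .75, 1.06 | 77%, 76% |
| 25% plus 2-SD rules | 30% | 26.2 | .275, .388 | .77, 1.09 | 74%, 73% |
| Partial test, 23 of 34 | 32% | 25.4 | .279, .395 | .79, 1.11 | 73%, 71% |
| Partial test, listed counts | 38% | 23.2 | .292, .413 | .82, 1.16 | 69%, 67% |

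**How much is due to what.** From 30 to 25.4 is a drop of 4.6 per condition. Of this, 1.9 (30 − 28.1) comes from how the 25% is applied to 150, and 2.7 (28.1 − 25.4) from losses the allowance does not name.

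**The case against.** The strongest reply is that the shortfall is small and its size poorly known.

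- About 40% of the drop at 32% loss (1.9 of 4.6) is the step from 25% of 150 to 30, not uncounted reasons. This stands. Measured from 28.1, the uncounted losses move the half-widths only from .265 to .279 and from .375 to .395.
- In the partial test mood and deception failures together were 6 of 34, below the 25% allowed, so on that evidence the allowance could absorb awareness of the aims as well. This stands too. Even so, adding the two 2-SD rules to that lower rate leaves 28.8, not 30.
- The base is 34 people, and the interval of 17% to 51% includes both 20% and 25%. The listed reasons sum to 13 while the net loss is 11; overlap may explain it, but the text does not say. So 32% is a planning value and not a forecast.
- The sample size is presented as balancing feasibility against precision, power is given only for completeness, and the mood and awareness removals are confined to the initial analyses. This limits the consequence. It does not rescue the figures, since the SAP computes its precision with mood failures already removed.

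A reader might go further and infer that the SAP's own exclusion rules will cause a loss of a third. The documents do not show that: the losses beyond mood and deception failure are put down to a software malfunction, which may not recur, and to the exclusion of error trials, which is trial-level wording. A reader might also infer that alcohol will raise the losses. The documents give no figure for this, and because the cut-offs are relative to the sample's own mean and SD, slower or less accurate responding need not exclude more people.

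**Conclusion.** The point holds at moderate size. The allowance names one loss, the SAP's rules create others, and 30 per condition needs a total loss of 20%, which is less than the SAP allows for mood failure alone. That much rests on the documents without any partial-test data.

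How far below 30 the analysis set falls is uncertain. The scenarios run from 28.8 down to 23.2 per condition. At the partial test's 32% the half-widths are about 9% wider than stated, and power at the stated effects is 73% and 71%. These figures assume equal losses across conditions; those using the 2-SD rules also assume normality and independence.

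A reader might infer that the study is too small, or that a narrow expected n can be named. Neither follows: the plan does not rest on significance testing, feasibility is part of its rationale, and the evidence supports a range only.

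**What to change.** In the SAP, Power and Sample Size Considerations, replace the mood-failure allowance with one total loss allowance that covers mood-induction failure, awareness of the aims, the latency and error-rate exclusions, and missing Stroop data. Restate the figures for 150 enrolled over a total loss of about 25% to 38%:

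- n per condition: 28 down to 23
- 68% half-widths: .265 to .292 (alcohol effect) and .375 to .413 (interaction)
- detectable effects: about .75 to .82 and 1.06 to 1.16

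Align the oversampling sentences in the protocol (Study Participants; Potential Problems) with this. In Preliminary Data, explain why 23 were analysed when 34 − 2 − 6 − 5 = 21, stating any overlap between reasons.

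The cost is wording in two documents and slightly less favourable stated figures. No extra enrolment is proposed.
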